### 9.1.5.2. Meningitis

For the further evaluation of the safety signal of meningitis in the investigational vaccine groups, all cases of meningitis occurring during the study will be reported as a SAE.

## 9.2. Events or outcomes not qualifying as adverse events or serious adverse events

### 9.2.1. Pregnancy

Female subjects who become pregnant after the vaccination will not receive the sporozoite challenge may continue the study for safety follow-up only, at the discretion of the investigator.

While pregnancy itself is not considered an AE or SAE, any adverse pregnancy outcome or complication or elective termination of a pregnancy for medical reasons will be recorded and reported as an AE or a SAE.

Note: The pregnancy itself should always be recorded on an electronic pregnancy report.

The following should always be considered as SAE and will be reported as described in Sections 9.4.1 and 9.4.3:

- Spontaneous pregnancy loss, including:
  - Spontaneous abortion, (spontaneous pregnancy loss before/at 22 weeks of gestation),
  - Ectopic and molar pregnancy,
  - Stillbirth (intrauterine death of fetus after 22 weeks of gestation).
- Any early neonatal death (i.e., death of a live born infant occurring within the first 7 days of life).
- Any congenital anomaly or birth defect (as per [CDC MACDP] guidelines) identified in the offspring of a study subject (either during pregnancy, at birth or later) regardless of whether the fetus is delivered dead or alive. This includes anomalies identified by prenatal ultrasound, amniocentesis or examination of the products of conception after elective or spontaneous abortion.

Furthermore, any SAE occurring as a result of a post-study pregnancy AND considered by the investigator to be reasonably related to the study vaccine will be reported to GSK Biologicals as described in Section 9.4.3. While the investigator is not obligated to actively seek this information from former study participants, he/she may learn of a pregnancy through spontaneous reporting.

**9.3. Detecting and recording adverse events, serious adverse events and pregnancies****9.3.1. Time period for detecting and recording adverse events, serious adverse events and pregnancies**

*Only for the P-Fx and NP-Fx groups:*

All AEs starting within 21 days following administration of the dose of study vaccine (Day 1 to Day 21) must be recorded into the appropriate section of the eCRF, irrespective of intensity or whether or not they are considered vaccination-related.

SAEs that are related to the study vaccine will be collected and recorded from the time of the receipt of study vaccine until the subject is discharged from the study.

*For all subjects:*

The time period for collecting and recording AEs post-challenge will begin at the first day of challenge (Day 22) up to 29 days post-challenge (Day 50).

The time period for collecting and recording AEs of specific interest (pIMDs and meningitis) will begin at Day 1 (for P-Fx and NP-Fx groups)/the first day of sporozoite challenge (Day 22) (for infectivity control group) and will end at the last study visit (Day 190 for the P-Fx and NP-Fx groups/Day 50 for the infectivity control group). See Section 9.4 for instructions on reporting of pIMDs.

The time period for collecting and recording SAEs will begin at Day 1 (for P-Fx and NP-Fx groups)/the first day of sporozoite challenge (Day 22) (for infectivity control group) and will end at the last study visit (Day 190 for the P-Fx and NP-Fx groups/Day 50 for the infectivity control group) for each subject. See Section 9.4 for instructions on reporting of SAEs.

All AEs/SAEs leading to withdrawal from the study will be collected and recorded from Day 1 (for P-Fx and NP-Fx groups)/the first day of sporozoite challenge (Day 22) (for infectivity control group).

In addition to the above-mentioned reporting requirements and in order to fulfil international reporting obligations, SAEs that are related to study participation (i.e., protocol-mandated procedures, invasive tests, a change from existing therapy) or are related to a concurrent GSK medication/vaccine will be collected and recorded from the time the subject consents to participate in the study (screening) until she/he is discharged from the study.

The time period for collecting and recording pregnancies will begin at Day 1 (for P-Fx and NP-Fx groups)/the first day of sporozoite challenge (Day 22) (for infectivity control group) and will end at the last study visit (Day 190 for the P-Fx and NP-Fx groups/Day 50 for the infectivity control group). See Section 9.4 for instructions on reporting of pregnancies.

An overview of the protocol-required reporting periods for AEs, SAEs and pregnancies is given in [Table 20](#).

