## **1.2. Rationale for the study and study design**

### **1.2.1. Rationale for the study**

This follow-up study (MALARIA-102) to the MALARIA-092 study will be conducted at WRAIR and is designed to evaluate the waning efficacy with the fractional schedules and to confirm if protection can be extended with an additional Fx dose.

In this booster study, vaccinated subjects from the MALARIA-092 study (previously protected or unprotected following CHMI) will receive a booster and undergo a second CHMI three to four weeks after vaccination.

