##### **6.4.1.1. Contraindications to malaria challenge**

The only absolute contraindication to mosquito challenge is pregnancy. If this occurs after immunization but before undergoing challenge, the subject must not be challenged and she will be followed for the duration of the study or pregnancy whichever is longer.

A subject with a minor illness but who does not have fever during the pre-challenge assessment may be challenged at the discretion of the investigator. If the subject is

moderately to severely ill with fever on the day of the challenge, he/she will not be challenged. Challenge can be performed within the time window defined in [Table 6](#) and [Table 7](#), at the discretion of the investigator if the subject becomes well. Subjects who will not be challenged will be followed for the duration of the study.

Any conditions which according to the judgment of the investigator would make the challenge unsafe.

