**Table 6 Intervals between study visits for the P-Fx and NP-Fx groups**

Interval	Optimal length of interval*	Allowed interval**
Screening #1 → Visit 1	1 to 90 days	-
Visit 1 → Visit 2	7 days	6-8 days
Visit 1 → Visit 3 (challenge)	21 days	21-28 days
Visit 3 → Visit 22	28 days	21-35 days
Visit 22 → Visit 23	140 days	126-154 days

\*Whenever possible the investigator should arrange study visits within this interval.

\*\*Subjects may not be eligible for inclusion in the Per-Protocol Set (PPS) for analysis of immunogenicity and efficacy if they make the study visit outside this interval.

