5.5. Analysis of safety and reactogenicity

5.5.1. Analysis of safety and reactogenicity planned in the protocol

The analysis of safety will be performed on the ITTS.

For the P-Fx and NP-Fx groups:

- The percentage of subjects with at least one local AE (solicited and unsolicited), with at least one general AE (solicited and unsolicited) and with any AE during the 7-day or 21-day follow-up period after the booster Fx dose will be tabulated with exact 95% CI. Same computations will be done for grade 3 AEs, for any AEs considered related to vaccination and for any grade 3 AEs considered related to vaccination.
- The percentage of subjects reporting each individual solicited local AE (any grade and grade 3) and each individual solicited general AE (any grade, grade 3, any related, grade 3 related, resulting in medically attended visit) during the 7-day follow-up period (Days 1-7) after the booster Fx dose will be tabulated for each group, with exact 95% CI.
- For fever (defined as temperature $\geq 37.5^{\circ}\text{C}/99.5^{\circ}\text{F}$ for oral, axillary or tympanic route), the number and percentage of subjects reporting fever by half degree ($^{\circ}\text{C}$) cumulative increments during the first seven days (Days 1-7) after the booster Fx dose will be tabulated. Similar tabulations will be performed for any fever with a causal relationship to vaccination and grade 3 ($> 39.0^{\circ}\text{C}$) causally related fever. The maximum temperature reported over the 7-day follow-up period will be tabulated.
- The percentage of subjects reporting unsolicited AEs within 21 days (Days 1-21) after the booster Fx dose will be tabulated by group and by MedDRA preferred term with exact 95% CI. Similar tabulation will be done for grade 3 unsolicited AEs, for any causally related unsolicited AEs and for grade 3 causally related unsolicited AEs.
- The percentage of subjects using concomitant medication (any medication, any antipyretic and any prophylactic medication, respectively) during the 7-day follow-up period after vaccination will be summarized by group.

For all subjects:

- The percentage of subjects reporting AEs during 29 days after the sporozoite challenge (Day 22-Day 50) will be tabulated by group and by MedDRA preferred term with exact 95% CI. Similar tabulation will be done for grade 3 unsolicited AEs, for any causally related unsolicited AEs and for grade 3 causally related unsolicited AEs post challenge.

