9.1.3.4. Onset day

The onset day for an event (e.g. AE, medication, vaccination) is the number of days between the study vaccination and the start date of the event. This is 1 for an event occurring on the same day as a vaccination (and reported as starting after vaccination).

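### The post-vaccination and post-challenge AE windows join only if challenge falls exactly 21 days after vaccination, but challenge is allowed up to Day 29 and neither document says how the windows then apply

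*Protocol*

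**What the plan says.** Ordinary AEs are collected in two windows, both set in Protocol 9.3.1.

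- **After vaccination (P-Fx and NP-Fx):** "All AEs starting within 21 days following administration of the dose of study vaccine (Day 1 to Day 21) must be recorded". The diary instruction in Protocol 6.6.17 covers the same 21 days.
- **After challenge (all subjects):** "AEs post-challenge will begin at the first day of challenge (Day 22) up to 29 days post-challenge (Day 50". The endpoint in Protocol 11.2 and SAP 3.2.2 counts the challenge day plus the next 28 days. The table in Protocol 11.11 and SAP 5.5.1 adds study days: "The percentage of subjects reporting AEs during 29 days after the sporozoite challenge (Day 22-Day 50) will be tabulated by group".

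The interval from vaccination to challenge is not fixed. Protocol Table 6, repeated as SAP Table 1, reads "Visit 1 → Visit 3 (challenge) 21 days 21-28 days": 21 days is optimal and 21 to 28 days is allowed. Protocol 1.2.1 says that subjects "will receive a booster and undergo a second CHMI three to four weeks after vaccination". Protocol 6.4.1.1 foresees a delay for a subject who is ill with fever on the planned day: "Challenge can be performed within the time window defined in" Tables 6 and 7.

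The only onset-day rule is in SAP 9.1.3.4: "The onset day for an event (e.g. AE, medication, vaccination) is the number of days between the study vaccination and the start date". No onset day relative to challenge is defined.

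Some events are collected from Day 1 in vaccinees without a break: SAEs, pIMDs, meningitis, and AEs leading to withdrawal (Protocol 9.3.1). Intercurrent medical conditions are checked at every visit after vaccination and entered in the eCRF, but not as AEs (Protocol 7.7).

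**The concern.** The first window is tied to vaccination. The second is tied to challenge but also carries fixed study-day labels. The labels are correct only at the optimal interval, and the allowed interval extends only later, so every permitted departure from 21 days breaks the join. Neither document says whether Day 22 and Day 50 are nominal or literal, or which window covers the days before a later challenge.

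Both windows feed secondary safety endpoints. At stake is either a stretch in which recently boosted subjects have no rule for ordinary AEs, or a post-challenge table that does not match its own endpoint. An AE that was never collected cannot be reliably recovered at analysis, so a collection gap has to be closed in the protocol and not only in the SAP.

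**Working it through.** **Inputs.** Vaccination is on Day 1. The allowed interval to challenge is 21 to 28 days (Protocol Table 6). The post-vaccination window is Days 1 to 21 and the post-challenge window is labelled Day 22 to Day 50 (Protocol 9.3.1). The endpoint is the challenge day plus 28 days (Protocol 11.2).

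**Formulas** (inclusive days, interval *d*):

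- challenge day *c* = 1 + *d*
- end of the endpoint window = *c* + 28
- days between the windows if the second starts at challenge = *c* − 22
- post-challenge days kept by a literal Day 22 to Day 50 cut = 50 − *c* + 1

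**The plan's own figure.** With *d* = 21: *c* = 22, the end is 22 + 28 = Day 50, the length is 50 − 22 + 1 = 29 days and the gap is 0. The stated window reproduces, at this interval only.

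**Across the allowed interval:**

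| Interval (days) | Challenge (study day) | Endpoint window | Gap if the window starts at challenge | Post-challenge days kept if Day 22–50 is literal |
|---|---|---|---|---|
| 21 | 22 | 22–50 | 0 | 29 |
| 22 | 23 | 23–51 | 1 | 28 |
| 23 | 24 | 24–52 | 2 | 27 |
| 24 | 25 | 25–53 | 3 | 26 |
| 25 | 26 | 26–54 | 4 | 25 |
| 26 | 27 | 27–55 | 5 | 24 |
| 27 | 28 | 28–56 | 6 | 23 |
| 28 | 29 | 29–57 | 7 (Days 22–28) | 22 |

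**Reading A, nominal labels.** Day 22 means the day of challenge and Day 50 means 28 days later. The table agrees with the endpoint. For a Day 29 challenge, an ordinary non-serious AE starting on Days 22 to 28 is after the first window and before the second.

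**Reading B, literal study days.** Collection runs on from Day 21 to Day 22 without a gap. For a Day 29 challenge, the table counts 7 pre-challenge days (Days 22–28) as post-challenge, keeps 22 of 29 post-challenge days (76%) and drops Days 51–57. This contradicts the endpoint.

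**Controls.** They have no vaccination day, and their only interval before challenge runs from screening (Protocol Table 7). Their challenge therefore defines Day 22, and neither effect arises. An onset day counted from vaccination is, however, undefined for them.

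**Other provisions that might bridge the gap.** The 30-day rule in Protocol 9.5.1.1 follows AEs already documented; it does not collect new ones. The active question in Protocol 9.3.3.1 asks about changes since the previous visit, so an event might be mentioned, but that section sets no collection period. Protocol 7.7 records conditions in connection with per-protocol eligibility.

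**The case against.** The strongest objection is that the documents favour Reading A, so the post-challenge table is probably right as intended. The endpoint is counted from the challenge day. The table sentence speaks of 29 days after challenge and gives the study days only in parentheses. Table 6 puts Visit 22, labelled Day 50, 28 days after Visit 3. Controls carry the same day labels without having a Day 1. On that reading both endpoints are fully observed as defined, and collecting AEs between them extends the scope.

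Most of this stands, and it limits the point. It does not remove it: under Reading A a boosted subject in active follow-up has up to 7 days with no rule for ordinary AEs, and nothing indicates that this was intended.

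A reader might infer more than the documents support in four ways.

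- **Gap and shifted table together.** Both occur only if collection is anchored on challenge and the table is cut at literal days. Neither document says so. The vaccination-based onset day makes it possible, but that rule is in the SAP's annex of standard rules and is not stated to select events for the post-challenge table.
- **No non-serious AE is collected in the gap.** This is too broad: non-serious pIMDs and non-serious AEs leading to withdrawal are collected from Day 1.
- **The missed AEs are those of subjects who were ill on the planned day.** The first window goes by onset, so an illness that began by Day 21 is collected. Only onsets from Day 22 are exposed, and no figure shows that these would be selective.
- **AEs of late parasitemia are cut off.** This needs Reading B. Even then, Day 50 is 50 − 29 = 21 days after a Day 29 challenge, while Protocol 6.4.1.5 gives a usual pre-patent period of 9–12 days, 7–18 days in earlier controls and 25 days at the longest. Some late cases could be missed, but not the period as a whole.

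**Conclusion.** The point holds as an unresolved mismatch between the AE windows and the allowed challenge interval. For a vaccinee challenged after Day 22, the plan leads to one of two results:

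- a gap of up to 7 days in ordinary AE collection (nominal labels, the better supported reading); or
- a post-challenge table that includes up to 7 pre-challenge days and omits as many of the 29 endpoint days (literal labels).

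These are per-subject maxima at an interval of 28 days. They are zero at 21 days, which is the optimal interval. The number of subjects challenged later is not given, so the effect on group percentages cannot be estimated. The range of 0 to 7 days assumes that the allowed interval is kept. A challenge outside it may remove a subject from the per-protocol set, but safety is analysed on the ITTS, so that subject would stay in the safety tables.

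The primary endpoint, the time-to-onset analysis (which already uses the actual challenge date, Protocol 11.9 and SAP 5.3.1) and the power are not affected. All analyses are declared descriptive. This is an inexpensive improvement to safety collection and not a threat to the trial's conclusions.

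**What to change.** **Collection.** In Protocol 9.3.1, Table 20 and the diary instruction in 6.6.17, collect unsolicited AEs continuously from Day 1 to the day before the actual challenge. Keep Days 1 to 21 as the endpoint table, and list AEs starting between Day 22 and a later challenge separately. State an end date for a vaccinee who is never challenged.

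**Analysis.** In Protocol 11.11 and SAP 5.5.1, define the post-challenge window as actual challenge date to challenge date + 28 for every subject, and say that Day 22 and Day 50 are nominal. In SAP 9.1.3.4, add an onset day counted from challenge, for post-challenge AEs and for all AEs in controls.

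**Cost.** Wording in both documents, and at most 7 more diary days for vaccinees challenged late within the allowed interval. No extra visit is needed, because the unsolicited-AE diary is already returned at the challenge visit.

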**Table 20 Reporting periods for collecting safety information**

Event	SCR*							Study Conclusion**
		V1 D1	V7 D7	V3 D21	V7 D22	V22 D30	V22 D50	
Solicited local and general AEs post-vaccination								
Unsolicited AEs post-vaccination								
AEs post-challenge								
SAEs (all, fatal, related) Pregnancies AEs of specific interest#								
SAEs related to study participation or concurrent GSK medication/vaccine								

SCR = screening; D = Day; V = Visit

\*i.e., consent obtained.

\*\*Visit applicable for all groups except for the infectivity control subjects (note that Day 50 is the study end for infectivity controls)

#pIMDs and meningitis

### 9.3.2. Post-study adverse events and serious adverse events

A post-study AE/SAE is defined as any event that occurs outside of the AE/SAE reporting period defined in [Table 20](#). Investigators are not obligated to actively seek AEs or SAEs in former study participants. However, if the investigator learns of any SAE at any time after a subject has been discharged from the study, and he/she considers the event reasonably related to the study vaccine, the investigator will promptly notify the Study Contact for Reporting SAEs.

### 9.3.3. Evaluation of adverse events and serious adverse events

#### 9.3.3.1. Active questioning to detect adverse events and serious adverse events

As a consistent method of collecting AEs, the subject should be asked a non-leading question such as: *“Have you felt different in any way since receiving the vaccine or since the previous visit?”*

When an AE/SAE occurs, it is the responsibility of the investigator to review all documentation (e.g., hospital progress notes, laboratory and diagnostics reports) relative to the event. The investigator will then record all relevant information regarding an AE/SAE in the eCRF. The investigator is not allowed to send photocopies of the subject's medical records to GSK Biologicals instead of appropriately completing the eCRF. However, there may be instances when copies of medical records for certain cases are requested by GSK Biologicals. In this instance, all subject identifiers will be blinded on the copies of the medical records prior to submission to GSK Biologicals.

The investigator will attempt to establish a diagnosis pertaining to the event based on signs, symptoms, and/or other clinical information. In such cases, the diagnosis should be documented as the AE/SAE and not the individual signs/symptoms.

### 9.3.3.2. Assessment of adverse events

#### 9.3.3.2.1. Assessment of intensity

The intensity of the following solicited AEs will be assessed as described:

**Table 21 Intensity scales for solicited symptoms**

Adverse Event	Intensity grade	Parameter
Pain at injection site	0	None
	1	Mild: Any pain neither interfering with nor preventing normal every day activities
	2	Moderate: Painful when limb is moved and interferes with every day activities.
	3	Severe: Significant pain at rest. Prevents normal every day activities.
Redness at injection site		Record greatest surface diameter in mm
Swelling at injection site		Record greatest surface diameter in mm
Fever*		Record temperature in °C/°F
Headache	0	Normal
	1	Mild: Headache that is easily tolerated
	2	Moderate: Headache that interferes with normal activity
	3	Severe: Headache that prevents normal activity
Fatigue	0	Normal
	1	Mild: Fatigue that is easily tolerated
	2	Moderate: Fatigue that interferes with normal activity
	3	Severe: Fatigue that prevents normal activity
Gastrointestinal symptoms (nausea, vomiting, diarrhea and/or abdominal pain)	0	Normal
	1	Mild: Gastrointestinal symptoms that are easily tolerated
	2	Moderate: Gastrointestinal symptoms that interfere with normal activity
	3	Severe: Gastrointestinal symptoms that prevent normal activity

\*Fever is defined as temperature  $\geq 37.5^{\circ}\text{C} / 99.5^{\circ}\text{F}$ . The preferred location for measuring temperature in this study will be the oral cavity.

The maximum intensity of local injection site redness and swelling will be scored at GSK Biologicals as follows:

0	:	0 mm
1	:	> 0 to $\leq$ 50 mm
2	:	> 50 mm to $\leq$ 100 mm
3	:	> 100 mm

The maximum intensity of fever will be scored at GSK Biologicals as follows:

0	:	< 37.5°C (< 99.5°F)
1	:	$\geq$ 37.5°C ( $\geq$ 99.5°F) to $\leq$ 38.0°C (100.4°F)
2	:	> 38.0°C (> 100.4°F) to $\leq$ 39.0°C (102.1°F)
3	:	> 39.0°C (102.1°F)

The normal ranges and toxicity grading for laboratory safety parameters used in this study are presented in [Table 22](#).

**Table 22      Toxicity grading scales for blood testing**

Adverse event	Intensity grade	Intensity*
Hemoglobin (males)	Normal range	$\geq 12.5 \text{ g/dL}$
	1	< 12.5 but $\geq 11.0 \text{ g/dL}$
	2	< 11.0 but $\geq 10.0 \text{ g/dL}$
	3	< 10.0 g/dL
Hemoglobin (females)	Normal range	$\geq 11.5 \text{ g/dL}$
	1	< 11.5 but $\geq 10.5 \text{ g/dL}$
	2	< 10.5 but $\geq 9.5 \text{ g/dL}$
	3	< 9.5 g/dL
Increase in leukocytes (WBC)	Normal range	$\leq 10\,799 \text{ cells/mm}^3$
	1	10\,800 – 15\,000 cells/mm 
	2	15\,001 – 20\,000 cells/mm 
	3	> 20\,001 cells/mm 
Decrease in leukocytes (WBC)	Normal range	$\geq 3200 \text{ cells/mm}^3$
	1	2500 - 3199 cells/mm 
	2	1500 - 2499 cells/mm 
	3	< 1500 cells/mm 
Decrease in platelets	Normal	$\geq 140\,000 \text{ cells/mm}^3$
	1	125\,000 – 139\,000 cells/mm 
	2	100\,000 – 124\,000 cells/mm 
	3	< 100\,000 cells/mm 
Alanine aminotransferase	Normal range	Below ULN (60 U/L for males; 40 U/L for females)
	1	1.1 - 2.5 x ULN
	2	2.6 - 5 x ULN
	3	> 5 x ULN
Aspartate aminotransferase	Normal range	Below ULN (40 U/L for males; 35 U/L for females)
	1	1.1 - 2.5 x ULN
	2	2.6 - 5 x ULN
	3	> 5 x ULN
Creatinine (males)	Normal range	$\leq 1.39 \text{ mg/dL}$
	1	1.4 - 1.79 mg/dL
	2	1.8 - 2.0 mg/dL
	3	> 2.0 mg/dL
Creatinine (females)	Normal range	$\leq 1.29 \text{ mg/dL}$
	1	1.3 - 1.69 mg/dL
	2	1.7 - 1.9 mg/dL
	3	> 1.9 mg/dL

ULN: upper limit of normal range

\*Grading scale adapted from [\[FDA guidance for industry: toxicity grading scale for healthy adult and adolescent volunteers enrolled in preventive vaccine clinical trials \(September 2007\)\]](#).

The investigator will assess the maximum intensity that occurred over the duration of the event for all unsolicited AEs (including SAEs) recorded during the study. The assessment will be based on the investigator's clinical judgement.

The intensity should be assigned to one of the following categories:

1 (mild)	= An AE which is easily tolerated by the subject, causing minimal discomfort and not interfering with everyday activities.
2 (moderate)	= An AE which is sufficiently discomforting to interfere with normal everyday activities.
3 (severe)	= An AE which prevents normal, everyday activities. In adults, such an AE would, for example, prevent attendance at work/school and would necessitate the administration of corrective therapy.

An AE that is assessed as Grade 3 (severe) should not be confused with a SAE. Grade 3 is a category used for rating the intensity of an event; and both AEs and SAEs can be assessed as Grade 3. An event is defined as 'serious' when it meets one of the pre-defined outcomes as described in Section [9.1.2](#).

